### *Secondary Performance Endpoints*

The secondary performance endpoint Time to Hemostasis was to evaluate the elapsed time between MANTA deployment and the first observed and confirmed arterial hemostasis. Mean Time to Hemostasis was 2 minutes and 23 seconds (Standard deviation: 6 minutes and 38 seconds; Median: 24 seconds; Minimum: 2 seconds; Maximum: 37 minutes and 10 seconds). For 37 subjects (74%), Time to Hemostasis was reported as  $\leq 1$  minute; for 10 subjects (20%), 1 to 10 minutes were required until hemostasis was achieved; and for 3 subjects (6%), more than 10 minutes and manual pressure were required until hemostasis achievement

The secondary performance endpoint Time to Ambulation was to evaluate the elapsed time between MANTA deployment and when ambulation is achieved. Mean Time to Ambulation was 44 hours and 10 minutes (Standard deviation: 25 hours and 7 minutes; Median: 43 hours and 34

minutes; Minimum: 3 hours and 42 minutes; Maximum: 142 hours and 1 minute). For 5 subjects (10%), Time to Ambulation was reported as less than 24 hours; for 28 subjects (56%) Time to Ambulation was between 24 and 72 hours; and for 6 subjects (12%) more than 72 hours were required until ambulation. Hemostasis was maintained during ambulation for all subjects with available data (n=41).

The secondary performance endpoint Treatment Success was to evaluate the number of subjects that had Hemostasis Success and no Major Complications reported. Treatment Success was achieved in 47 subjects (94%). Absence of Hemostasis Success, as well as presence of one or more Major Complications, occurred in the same 3 subjects.

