### **8.3.6 Missing Data**

It is highly unlikely that there will be missing data for Time to Hemostasis, Technical Success, Ambulation Success, Time to Ambulation, Treatment Success or Procedure Time. However, if any of these endpoints are missing, the worst value observed for any subject at the same study site will be imputed for the missing value.

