5 DATA CONVENTIONS AND DEFINITIONS

5.1 Handling of Missing Data

Missing data will not be imputed for safety endpoints. However, if more than 13 subjects in the Primary Analysis Cohort either die for a reason other than a Major Complication or are lost to follow up within 30 days of treatment, then the rate of Major Complications will also be estimated by the Kaplan-Meier method, to allow for subjects who are censored before a Major Complication can be observed. See Section 2.4.1 for further details.

For effectiveness endpoints, it is highly unlikely that there will be missing data for Time to Hemostasis, Technical Success, Ambulation Success, Time to Ambulation, Treatment Success or Procedure Time. However, if any of these data are missing (i.e., in the event that Time to Hemostasis cannot be evaluated because a surgical repair must be performed), the worst value observed for any subject at the same study site within each analysis cohort, will be imputed for the missing value. Missing data for a subject in the Primary Analysis Cohort will be imputed with the worst value observed for any Primary Analysis Cohort subject at the same study site, and missing data for a subject in the Roll-In Cohort will be imputed with the worst value observed for any roll-in subject at the same study site.

No other imputations will be carried out for missing data.

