6.2.2 Secondary Effectiveness Endpoints

The secondary endpoints are defined below. Summary statistics will be reported for each endpoint, but there will be no formal statistical test performed. Continuous variables will be summarized using descriptive summary statistics such as mean, median, standard deviation, minimum and maximum. Categorical variables will be summarized as counts and percentages.

Technical Success: A subject will be considered a Technical Success if percutaneous vascular closure is obtained with the MANTA device without the use of unplanned endovascular or surgical intervention.

Ambulation Success: A subject will be considered an Ambulation Success if he/she is able to ambulate for at least 20 feet/6 meters without re-bleeding.

Treatment Success: A subject will be considered a Treatment Success if he/she has Time to Hemostasis \leq 10 minutes and has no Major Complications (as defined above in 2.5.1).

Time to Ambulation: The elapsed time (in hours) between MANTA deployment (withdrawal of sheath from artery) and when ambulation is achieved (subject standing and walking at least 20 feet/6 meters without re-bleeding).

Procedure Time: The elapsed time (in minutes) from initial skin break (first needle insertion) to time when the post-deployment angiogram is completed.

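### Imputing the worst value observed at the site fails for the three yes/no success endpoints: a missing value becomes a success wherever no failure was observed

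*SAP*

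**What the plan says.** SAP 5.1 names the endpoints to which its effectiveness rule applies: "missing data for Time to Hemostasis, Technical Success, Ambulation Success, Time to Ambulation, Treatment Success or Procedure Time". It regards missing values as very unlikely, but if one occurs, "the worst value observed for any subject at the same study site within each analysis cohort, will be imputed for the missing value". Values are borrowed within the Primary Analysis Cohort or within the Roll-In Cohort, always from the same site. The section ends: "No other imputations will be carried out for missing data". Protocol 8.3.6 covers the same six endpoints: "the worst value observed for any subject at the same study site will be imputed for the missing value".

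Three of the six are yes/no by definition in SAP 6.2.2. The first turns on closure: "A subject will be considered a Technical Success if percutaneous vascular closure is obtained with the MANTA device", with rescue by surgery or by an endovascular step that was not planned ruled out. The second turns on walking: "A subject will be considered an Ambulation Success if he/she is able to ambulate for at least 20 feet/6 meters without re-bleeding". The third, Treatment Success, requires hemostasis within 10 minutes and no Major Complication. Neither document says that a missing yes/no value counts as failure. SAP 6.2.2 and Protocol 8.1.1 report these endpoints without a formal test.

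**The concern.** For a time endpoint, the worst observed value at a site is a long time, so borrowing it leans against the device. A yes/no endpoint has only two values. If every observed subject at a site succeeded, success is the only value available to borrow, and the missing subject is recorded as a success. At a site with one observed failure, the same subject is recorded as a failure. The score then depends on another patient's outcome and on how many patients the site happened to treat.

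The rule is also undefined at a site with no observed value in the cohort. That can happen, because Protocol 8.4 sets no minimum enrollment per site and the Roll-In Cohort has at most two subjects per operator. At stake is the accuracy of three secondary success rates in a study meant to support a PMA.

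**Working it through.** The plan attaches no figure to this rule, so there is none to reproduce. Its sample sizes do not enter the argument.

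**Inputs from the documents.** 5 to 25 sites (SAP 2.1); about 250 analyzable subjects and about 5% loss (SAP 3); no minimum per site and a cap of 50 treated subjects per site (Protocol 8.4).

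**Assumptions.** Equal site sizes (250/25 = 10 or 250/5 = 50), a common success probability p, and missingness q independent of outcome. The documents give neither p nor q for these endpoints. The 5% loss is borrowed for q.

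**Share of missing values scored as success.** For a missing subject at a site of m, each of the other m − 1 must be either missing or an observed success:

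share = [q + (1 − q)p]^(m − 1)

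With p = 0.95 and q = 0.05, the bracket is 0.05 + 0.95 × 0.95 = 0.9525.

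- 25 sites of 10: 0.9525^9 = 0.645 (64.4% in a simulation of 20,000 trials).
- 5 sites of 50: 0.9525^49 = 0.092.

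With p = 0.98 the bracket is 0.981. The shares are 0.981^9 = 0.841 and 0.981^49 = 0.391.

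**Expected reported rate** (p = 0.95, q = 0.05):

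| Method | Formula | 25 sites of 10 | 5 sites of 50 |
|---|---|---|---|
| Observed cases | p | 95.0% | 95.0% |
| Rule as written | (1 − q)p + q × share | 0.9025 + 0.05 × 0.645 = 93.5% | 0.9025 + 0.05 × 0.092 = 90.7% |
| Missing = failure | (1 − q)p | 90.3% | 90.3% |

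**Position against the observed-case rate.** At a site with no failure, the imputed site rate equals the observed rate, 100%. At any other site it is lower. With n observed subjects at a site, the chance of imputing success is p^n, which is not above p when n is at least 1. Under these assumptions the rule therefore does not exceed the observed-case rate on average. A single pooled result could edge above it if the missing values happened to fall mainly at sites without failures.

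**Treatment Success separately.** SAP 3 assumes 13% Major Complications, so Treatment Success is at most 87% under the plan's own assumption; the EU pre-market study observed 94%. The chance of no failure among ten observed subjects is 0.87^10 = 25% or 0.94^10 = 54%. For comparison, 0.95^10 = 60% and 0.98^10 = 82%.

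**Can missing values occur with no observed failure?** Protocol 1.4, on the EU study of 50 subjects, reports: "Hemostasis was maintained during ambulation for all subjects with available data (n=41"). So 50 − 41 = 9 subjects lacked that information and none of the rest was a failure. The time-to-ambulation categories there total 5 + 28 + 6 = 39.

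**The case against.** The strongest reply is that little will be missing and nothing turns on it. Protocol 7.7 makes the ability to walk the test distance a condition of discharge and records ambulation time whenever it occurs. A subject who never walks could be read as an observed failure. Technical Success is known at the procedure, and the SAP's own example of missing data, surgical repair, is already a Technical failure. The endpoints have no test and no performance goal. The Per Protocol Set drops subjects with missing Time to Hemostasis or a missing 30-day visit, and by-subject effectiveness listings are planned.

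Most of this stands and limits the reach. It does not remove the defect: the SAP does not say that a subject who never walks is a failure, and in-hospital deaths and recording gaps remain.

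A reader might infer more than the documents support:

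- **That the rule generally inflates success rates.** It is less conservative than counting missing as failure, but it cannot lift any site above its own observed rate.
- **That most missing subjects will be reported as successes.** This depends on site size. With 5 sites of 50 the share is about 9% at 95% success and 39% at 98%.
- **That the EU data show an 18-point effect (50/50 = 100% against 41/50 = 82%).** That is a different study, not said to use this rule. The contrast equates maintained hemostasis with Ambulation Success and carries 18% missingness into this trial.
- **That subjects lost before day 30 become Treatment Successes.** The documents do not say whether such a subject's Treatment Success is missing or is derived from the data in hand.
- **That missing subjects are the sicker ones.** This is plausible but not documented.

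**Conclusion.** The defect stands as a stated rule that gives an arbitrary result for three endpoints. Under the assumptions above with 25 sites, it reports about 3 points more than counting missing as failure (93.5% against 90.3%) and about 1.5 points less than the observed-case rate. With 5 large sites it almost coincides with missing as failure (90.7% against 90.3%). These figures move with the assumed success rate, missing rate and site sizes.

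Ambulation Success is the main exposure and Technical Success will rarely be missing. For Treatment Success the open question is how subjects lost before 30 days are scored. The EU experience shows only that missing ambulation data with no observed failures can occur; it does not estimate the effect here. Only reported secondary rates are affected, and neither primary decision changes. The correction is worth making because it is cheap.

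**What to change.** In SAP 5.1 and Protocol 8.3.6:

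1. Restrict the worst-observed-value rule to Time to Hemostasis, Time to Ambulation and Procedure Time.
2. Count missing Technical, Ambulation and Treatment Success as non-success in the main summary, and show the observed-case rate and the number missing beside each.
3. State how deaths or exits before ambulation are scored for Ambulation Success, and how exits before 30-day Major Complication status is known are scored for Treatment Success.

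This takes a few sentences in each document and no new data. Reported success rates may be a few points lower. SAP 5.1 does not impute safety endpoints, so a subject lost early could be a Treatment non-success yet show no event in the crude Major Complication rate. The Treatment Success table therefore needs a note explaining how its denominator and scoring differ from that rate.

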5.2 Poolability Analysis and Stratification

Analyses of the primary effectiveness and primary safety endpoints will be performed to assess the comparability of study sites. Sites with fewer than 5 subjects each will be pooled into a composite site.

Time to Hemostasis in the Primary Analysis Cohort population will be analyzed by a one-way analysis of variance that includes the effect of the study site. If the study site means differ ($p<0.15$) then additional analyses will be performed to explore the cause of the difference, in particular if the differences are caused by differences in some baseline factor.

Major Complications in the Safety population will be analyzed by Pearson's chi square to assess if the Major Complication rates differ among study sites. If the study site rates differ ($p<0.15$) then additional analyses will be performed to explore the cause of the difference, in particular if the differences are caused by differences in some baseline factor.

Stratified analyses will not be performed.

5.3 Covariates

As a supportive analysis, a covariate analysis will be conducted to assess the impact of various factors on the primary effectiveness endpoint. The following covariates will be examined:

- Gender
- Race
- Ethnicity
- Age Category

- Procedure type (e.g., TAVI, EVAR)
- MANTA device size
- Index device type (Manufacturer/Brand)
- Effective puncture size
- Sheath to femoral artery ratio (SFAR)

For each categorical covariate, Time to Hemostasis in the Primary Analysis Cohort population will be analyzed by a one-way analysis of variance that includes the effect of the covariate. If the subgroup means differ ($p<0.05$) then additional analyses will be performed to explore the cause of the difference, in particular if the differences are caused by another demographic factor. Major Complications in the Safety population will be summarized by levels of the covariate only.

For continuous covariates (SFAR), Time to Hemostasis in the Primary Analysis Cohort population will be analyzed by univariate regression. If the regression is significant ($p<0.05$) then additional analyses will be performed to explore the cause. Association of SFAR with Major Complications, Minor Complications and VARC-2 Major Vascular Complications will be examined through odds ratio analysis (see 6.3.3).

5.4 Subgroup Analyses

There are no subgroup analyses planned for this clinical trial.

5.5 Standard Calculations

5.5.1 Age

Age will be calculated as the number of completed years between the subject's birth date and the date of informed consent.

5.5.2 BMI

Body Mass Index will be calculated as the subject's weight in kilograms divided by height in meters squared (kg/m^2).

5.5.3 Clinical Trial Duration

Clinical trial duration will be calculated as the total number of days each subject is in the clinical trial.

$$\text{Duration} = (\text{Date of subject completion, death or withdrawal} - \text{Date of Procedure}) + 1$$

6 STATISTICAL ANALYSIS METHODS

6.1 Summarizing and Tabulating Collected Data

All data from this clinical trial will be provided in data listings by site, subject, and time point, as applicable.

Continuous and categorical variables will be summarized by descriptive statistics. Standard descriptive statistics for continuous variables will be the number of observations, mean, median, standard deviation, minimum and maximum. Standard descriptive statistics for categorical variables will be counts and percentages; percentages will be computed relative to the size of the reference population. 95% confidence intervals will also be provided where appropriate.

6.1.1 Subject Disposition and Withdrawals

There will be a detailed accounting of all subjects who sign an informed consent to participate in this trial. The number of subjects within each of the following groups will be summarized in total and by site: signed informed consent, intra-procedure screen failures, discontinued, and completing the study according to the protocol.

Reasons for discontinuations will be summarized by site using the following categories:

- Subject is lost to follow up
- Adverse event
- Explantation of the device
- Subject voluntarily withdraws
- Subject is withdrawn by the Investigator or Sponsor
- Sponsor or Investigator terminated study
- Death
- Other

In addition, there will be a listing of all discontinued subjects, which will include site, reason for discontinuation, and duration of study participation before discontinuation.

6.1.2 Protocol Deviations

The deviations occurring during the clinical trial will be determined to be major or minor by the Sponsor and data management group prior to database lock and will be summarized descriptively. A by-subject listing of all deviations will also be prepared. Categories of protocol deviations include:

- Informed Consent Procedure
- Inclusion/Exclusion
- Concomitant Medication/Therapy
- Laboratory Assessments/Procedures
- Study Procedures
- SAE Reporting/UADE Reporting
- Visit Schedule/Interval
- Other

6.1.3 Demographics and Other Baseline Characteristics

Demographics (age, gender, race, and ethnicity) and baseline characteristics (height in cm, weight in kg, BMI) will be summarized by descriptive statistics.

Prior surgical history events of interest (CABG, PCI, Pacemaker/ICD, Neurovascular Intervention, and Peripheral Intervention) and baseline laboratory tests of interest (creatinine, hematocrit, hemoglobin, INR, platelets, and urea nitrogen) will also be summarized by descriptive statistics.

All clinical examination results, medical history, and baseline laboratory tests (reported in SI units) will be provided as by-subject listings.

6.1.4 Concomitant Medications

Anti-coagulant and anti-platelet concomitant medications at baseline and during procedure will be summarized by generic drug name.

All concomitant medications will also be provided as by-subject listings.

6.2 Analysis of Effectiveness Data

6.2.1 Primary Effectiveness Endpoint

Time to Hemostasis is defined to be the elapsed time between MANTA deployment (withdrawal of sheath from artery) and first observed and confirmed arterial hemostasis (no or minimal subcutaneous oozing and the absence of expanding or developing hematoma). The mean Time to Hemostasis (in minutes) will be presented along with the one-sided upper 97.5% confidence bound. If this upper confidence bound is less than 10 minutes, the study will have met its primary effectiveness objective.

6.2.2 Secondary Effectiveness Endpoints

The secondary endpoints are defined below. Summary statistics will be reported for each endpoint, but there will be no formal statistical test performed. Continuous variables will be summarized using descriptive summary statistics such as mean, median, standard deviation, minimum and maximum. Categorical variables will be summarized as counts and percentages.

Technical Success: A subject will be considered a Technical Success if percutaneous vascular closure is obtained with the MANTA device without the use of unplanned endovascular or surgical intervention.

Ambulation Success: A subject will be considered an Ambulation Success if he/she is able to ambulate for at least 20 feet/6 meters without re-bleeding.

Treatment Success: A subject will be considered a Treatment Success if he/she has Time to Hemostasis \leq 10 minutes and has no Major Complications (as defined above in 2.5.1).

Time to Ambulation: The elapsed time (in hours) between MANTA deployment (withdrawal of sheath from artery) and when ambulation is achieved (subject standing and walking at least 20 feet/6 meters without re-bleeding).

Procedure Time: The elapsed time (in minutes) from initial skin break (first needle insertion) to time when the post-deployment angiogram is completed.

6.2.3 Procedural and Discharge Data

The secondary endpoints are defined below. Summary statistics will be reported for each endpoint, but there will be no formal statistical test performed. Continuous variables will be summarized using descriptive summary statistics such as mean, median, standard deviation, minimum and maximum. Categorical variables will be summarized as counts and percentages. Procedure sheath size, index device, index device size, MANTA size, target artery, target artery diameter, pre-deployment ACT, pre-deployment blood pressure, use of adjunctive methods for hemostasis or oozing, thrombus, and post-deployment angiogram results will also be summarized by endovascular procedure.

Effective puncture size (EPS) (mm): Derived from the combination of procedure sheath brand/size and index device/size, based on an algorithm developed by the sponsor. The algorithm is attached in Appendix B.

Endovascular procedure type: As completed on the eCRF, either TAVI, EVAR, Impella, or Other.

Procedure sheath brand: Derived from the sheath size/brand from the eCRF.

Procedure sheath size (F): As completed on the eCRF.

Index device manufacturer/brand: Derived from the Large Bore Device Used: Brand and Manufacturer from the eCRF.

Index device size (mm): As completed on the eCRF as Large Bore Device Used: Size (units).

MANTA size: As completed on the eCRF, either 18F or 14F.

Target artery: As completed on the eCRF, either Left Common Femoral Artery or Right Common Femoral Artery.

Target artery diameter (mm): As completed on the eCRF as recorded from baseline CTA.

Sheath to femoral artery ratio (SFAR): Calculation is as follows: $(EPS / 3.0)mm / (\text{target artery diameter})mm$

Pre-deployment ACT (sec): As completed on the eCRF.

Pre-deployment systolic and diastolic blood pressure (mmHg): As completed on the eCRF.

Use of adjunctive methods to obtain arterial hemostasis: Instances of need for adjunctive methods to achieve arterial hemostasis summarized by method, either manual compression, contralateral balloon, mechanical device, stent-graft, surgical repair, or other.

Use of adjunctive methods for treating oozing: Instances of subcutaneous oozing summarized by treatment, either light manual pressure, light mechanical pressure, sand bag, pressure dressing, or other.

Any thrombus observed on the MANTA components: As completed on the eCRF as whether thrombus was observed after removal, yes or no, and which component(s) were affected.

Post-deployment angiogram results: As completed on the eCRF, either target artery patent at MANTA deployment site, stenosis <50% at MANTA deployment site, stenosis ≥50% at MANTA deployment site, or other.

Time to discharge post-MANTA deployment: The elapsed time (in hours) from MANTA deployment (withdrawal of sheath from artery) and when subject is discharged.

Time to discharge post-ambulation: The elapsed time (in hours) from MANTA deployment (withdrawal of sheath from artery) and when ambulation is achieved (subject standing and walking at least 20 feet/6 meters without re-bleeding).

Mean ABI scores: Collected and summarized at baseline, post-procedure, discharge, and follow-up.

Ultrasound evaluations as evaluated by the VasCore Core Lab: Collected and summarized at post-procedure and follow-up, defined as:

- CFA PSV summary statistics, counts of CFA stenosis categories (patent, 50-99%, Occluded, Unknown, N/A), SFA PSV summary statistics
- Counts of arterial venous fistula, intimal artery defect, or mass present (if mass reported, type and size)
- Counts of patent CFV, CFV acute thrombus, patent proximal femoral vein, proximal femoral vein acute thrombus present (yes, no, unknown, N/A)

If a subject underwent more than one ultrasound for a scheduled visit, the latest result will be used for analysis.

Device deficiencies: Instances of device deficiency will be summarized by type of deficiency experienced as detailed on the Device Deficiency eCRF and by MANTA device size.

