### **7.7. Post-Procedure Evaluations**

1. It is recommended that 6 hours after removal of the access sheath, if the femoral access site is suitable for ambulation and if medically indicated, the subject should be asked to stand at bedside.
  - a. If the subject successfully stands with no or minimal oozing, the subject should be asked to walk 20 feet/6 meters. If the subject ambulates successfully, record the ambulation time on the eCRF.
  - b. If the subject is unable to walk 20 feet/6 meters or it is not medically advisable or logistically feasible to attempt ambulation, the subject should remain in bed. Attempt to ambulate the subject when medically indicated. When the subject ambulates successfully, record the ambulation time on the eCRF.
  - c. Lack of an ambulation attempt at 6 hours or ambulation at an earlier or later timepoint will not be considered a protocol deviation.
  - d. Following successful ambulation, the subject should be returned to bed. Perform access site checks per hospital standard of care following successful ambulation.

2. A duplex ultrasound will be performed prior to discharge (but no later than 48 hours post-MANTA deployment) to evaluate femoral blood flow. In addition, any suspected hematoma, pseudoaneurysm or AV fistula at the MANTA site should be confirmed with ultrasound.
3. Ipsilateral ankle/brachial index will be assessed prior to discharge.
4. When the subject is ready for discharge (at a minimum, defined as ability to walk 20 feet/6 meters, freedom from orthostatic hypotension [defined as stable blood pressure and heart rate after ambulating], ability to void and a stable access site without bleeding or expansion of a prior hematoma), record the date and time of discharge on the eCRF.

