2.8.2 Procedural and Discharge Data

The following data will be collected during the procedure and discharge and analysis will be performed on both the Safety Evaluation Set and the Per Protocol population. A separate analysis will also be performed for the Roll-in subjects.

1. Endovascular procedure type
2. Procedure sheath brand
3. Procedure sheath size (F)
4. Index device manufacturer/brand
5. Index device size (mm)
6. Effective puncture size (F)
7. MANTA size (14F or 18F)
8. Target artery (left or right)
9. Target artery diameter (mm)
10. Sheath to femoral artery ratio (SFAR)
11. Pre-deployment ACT (sec)
12. Use of adjunctive methods to obtain hemostasis
13. Use of adjunctive methods for treating oozing
14. Any thrombus observed on the MANTA components (Y/N)
15. Post-deployment angiogram results

- 16. Time to discharge post-MANTA deployment
- 17. Time to discharge post-ambulation
- 18. Mean ABI scores at baseline, pre-procedure, post-procedure, discharge, follow-up
- 19. Ultrasound findings post-procedure and at follow-up
- 20. Device deficiencies

Other procedure data will be reported in by-subject listings. Definitions for these data points are provided in Section 6.2.3.

2.8.3 *Exploratory Analyses*

Additional exploratory analyses will be performed as needed.

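### SAP 6.2.3 defines the ambulation-to-discharge interval as Time to Ambulation, and gives effective puncture size in a unit that its own SFAR formula does not fit

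*SAP*

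**What the plan says.** **Discharge interval.** SAP 2.8.2 lists two discharge intervals as separate items, 16 and 17; the second is "17. Time to discharge post-ambulation". SAP 6.2.3 defines the first as "Time to discharge post-MANTA deployment: The elapsed time (in hours) from MANTA deployment (withdrawal of sheath from artery) and when subject is discharged", which ends at discharge. It defines the second as "Time to discharge post-ambulation: The elapsed time (in hours) from MANTA deployment (withdrawal of sheath from artery) and when ambulation is achieved". SAP 6.2.2 defines the secondary effectiveness endpoint in matching terms: "Time to Ambulation: The elapsed time (in hours) between MANTA deployment (withdrawal of sheath from artery) and when ambulation is achieved".

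Protocol 7.7 has the site "record the ambulation time on the eCRF" and, at discharge, "record the date and time of discharge on the eCRF".

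**Effective puncture size.** SAP 2.8.2 (item 6) gives EPS in French. SAP 6.2.3 heads the same variable in mm and refers to Appendix B for the algorithm. The next use is SFAR = (EPS/3.0)/(target artery diameter), with numerator and denominator both marked mm. SFAR then serves as a continuous covariate for Time to Hemostasis (SAP 5.3) and as the predictor in the logistic regressions for complications (SAP 6.3.3).

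**The concern.** The SAP is the programming specification. For item 17 the written rule returns a different variable from the one named, and nothing else in the SAP corrects it. The clinical study report would then carry one quantity twice, once under a name suggesting that it measures the stay after ambulation, and the planned summary of that stay would be absent.

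For EPS, the two sections disagree on the unit. The division by 3.0 is the conversion from French to mm, so applying it to a value already in mm converts twice. At stake are the scale of the SFAR summaries, the SFAR slope for Time to Hemostasis, the SFAR odds ratios, and the labels of tables split by effective puncture size.

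**Working it through.** **(a) Discharge interval: the definitions side by side**

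| Variable | SAP section | Start | End | Unit |
|---|---|---|---|---|
| Time to Ambulation | 6.2.2 | MANTA deployment | ambulation achieved | hours |
| Time to discharge post-MANTA deployment | 6.2.3 | MANTA deployment | discharge | hours |
| Time to discharge post-ambulation | 6.2.3 | MANTA deployment | ambulation achieved | hours |

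Rows one and three are the same variable. Let A be the hours from deployment to ambulation and D the hours from deployment to discharge. The rule as written returns A; the name calls for D − A.

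The only ambulation figure to hand is from the EU study in Protocol 1.4: "Mean Time to Ambulation was 44 hours and 10 minutes", that is 44 + 10/60 = 44.17 h. The documents give no discharge times, so D is assumed here to show the behaviour:

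| Assumed D (h) | As written, A (h) | By its name, D − A (h) |
|---|---|---|
| 72 | 44.17 | 27.83 |
| 96 | 44.17 | 51.83 |
| 120 | 44.17 | 75.83 |

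The written rule does not respond to discharge time at all.

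*What can be recovered.* In subjects with both times, mean(D − A) = mean(D) − mean(A), so the mean can be rebuilt. The median, SD, minimum and maximum that 6.2.3 also plans cannot be read from the two separate summaries and would need the by-subject listings.

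*Missing ambulation times.* For a missing Time to Ambulation, SAP 5.1 says that "the worst value observed for any subject at the same study site within each analysis cohort, will be imputed for the missing value". It has no such rule for discharge time. If an imputed A entered the subtraction, the result could be negative. For example, with the EU study's maximum of 142 h 1 min as the imputed value and an assumed discharge at 72 h, D − A = 72 − 142.02 = −70.02 h. Missing ambulation times are plausible: the EU study's ambulation bands hold 5 + 28 + 6 = 39 of 50 subjects (78%), and data on hemostasis during ambulation existed for 41.

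**(b) EPS unit**

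Inputs:
- 1F = 0.33 mm (SAP list of abbreviations).
- 24.5F = 8.17 mm (Protocol 1.4, EU study, Performance).
- Minimum artery diameter 5 mm for the 14F device and 6 mm for the 18F device (Protocol 6.5.2).
- Maximum outer diameter 18F for the 14F device (Protocol 1.6.2).

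The protocol's own conversion is reproduced first: 24.5/3 = 8.17 mm. Division by 3.0 is therefore the French-to-mm conversion.

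For illustration, the sheath outer diameter is taken as EPS:

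| Puncture, artery | EPS in F: (F/3)/diameter | EPS in mm: (mm/3)/diameter |
|---|---|---|
| 24.5F (8.17 mm), 6 mm | 8.17/6 = 1.36 | (8.17/3)/6 = 0.45 |
| 18F (6.0 mm), 5 mm | 6.0/5 = 1.20 | (6.0/3)/5 = 0.40 |

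*Effect on the models.* If S′ = S/3, then βS = (3β)S′. The slope or log odds ratio per unit triples and its standard error triples with it, so the odds ratio per unit is cubed. The test statistic, p-value, direction and fit do not change.

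**The case against.** The strongest reply is that both slips are minor and that (b) may be no more than a stray label. The SFAR formula attaches mm to the result of the division, 2.8.2 says French, and the factor 3.0 makes sense only for French; the heading in 6.2.3 is the one entry out of line. If Appendix B outputs French, SFAR is computed correctly and only the heading is wrong. That stands, and the threefold error is conditional on it. The absence of Appendix B from the text reviewed is not a fault of the plan.

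The SFAR values above are also illustrative. EPS comes from a sponsor algorithm combining sheath and index device, and the first example pairs the largest EU-study sheath with this trial's smallest permitted artery for the 18F device. The factor of 3 does not depend on these choices; the absolute values do.

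On (a), the size of the discrepancy in this trial is unknown, since no discharge times are given. By-subject listings of procedural, discharge and effectiveness data are planned (SAP 2.8.1), so the correct interval could still be derived.

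On imputation, SAP 5.1 names six effectiveness endpoints and rules out any other imputation, and Protocol 7.7 makes ability to walk a minimum condition for discharge. Observed intervals should therefore rarely be negative. This is fair, but the analysis dataset may still hold an imputed Time to Ambulation, so restricting the interval to observed times is a harmless safeguard consistent with 5.1.

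None of this answers the core of (a): the definition as written yields the wrong variable.

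**Conclusion.** The point holds. Part (a) is certain on the text: the rule for Time to discharge post-ambulation reproduces Time to Ambulation for every subject and contains no discharge time. One planned descriptive summary would be mislabelled and the intended one missing.

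Part (b) is certain as a conflict between SAP 2.8.2 and 6.2.3. Its numerical effect is conditional: none on SFAR if EPS is held in French, which is the likelier intent, and a uniform factor of 3 if it is held in mm. The stored unit cannot be settled without Appendix B.

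The reach is limited to descriptive and supportive outputs. Neither primary endpoint test, neither performance goal and not the sample size is touched. Both parts should be corrected before programming.

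**What to change.** 1. In SAP 6.2.3, define Time to discharge post-ambulation as the date/time of discharge minus the date/time ambulation was achieved, in hours. State that it uses only subjects with both times observed, so that no imputed Time to Ambulation enters it.
2. State one EPS unit in SAP 2.8.2 and 6.2.3: French if the SFAR formula is kept, or mm with the division by 3.0 removed. Confirm the choice against the output of Appendix B, and label tables split by effective puncture size to match.

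The cost is two wording corrections to the SAP and a check of Appendix B. No new data are needed, since ambulation time and discharge date and time are already recorded.
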